5.4 LIFESTYLE CONSIDERATIONS

Not applicable.

5.5 SCREEN FAILURES

Screen failures are defined as participants who consent to participate in the clinical trial but are not subsequently assigned to the study intervention or entered in the study. A minimal set of screen failure information is required to ensure transparent reporting of screen failure participants, to meet the Consolidated Standards of Reporting Trials publishing requirements and to respond to queries from regulatory authorities. Minimal information includes demography, screen failure details, eligibility criteria, and any serious adverse event (SAE).

Individuals who do not meet the criteria for participation in this trial (screen failure) because of any failed criterion may be rescreened. Rescreened participants should be assigned the same participant number as for the initial screening.

5.6 STRATEGIES FOR RECRUITMENT AND RETENTION

This study is being conducted at a single site, the NIH CC. Participation of all racial and ethnic groups and genders will be actively encouraged. Recruitment will be supported by the Office of Patient Recruitment, which recruits participants for volunteer studies conducted at the NIH CC. IRB-approved flyers may also be posted for recruitment of participants.

Abbreviated Title: BSS Gut Microbiome

Version Date: 05 July 2024

Participants may be sent IRB-approved reminder emails, phone calls, and texts for administration and BSS, samples, surveys, and appointments.

5.6.1 Costs

There will be no costs to participants for participation in this study. Participants will be provided with collection kits with prepaid shipping for at-home stool, saliva, and urine collection, so there are no costs to the participant for those.

5.6.2 Compensation

Participants will be compensated as follows:

- \$20 for return of each stool sample with accompanying survey (maximum 6 times).
- \$20 for return of each set of saliva and urine samples (both required, maximum 6 times).
- \$40 for in-person visit for first dose of BSS and completion of all 8 doses (maximum once).
- \$30 per blood draw (maximum 6 times).
- \$300 for first colonoscopy (maximum once).
- \$500 for second colonoscopy (maximum once).

The minimum compensation (only stool samples and BSS doses) is \$160, and the maximum compensation (including all optional procedures) is \$1260. Payment will be provided as a gift card, check, debit card, direct deposit, or automated clearing house, given at the end of each visit (or upon receipt of send-in samples, as appropriate).

The NIH will cover some or all travel expenses related to participation in this study for participants who come to the NIH. The amount and form of these payments are determined by the NIAID Central Travel Policy for Research Protocol Participants. A copy of this policy will be provided to participants.

6 STUDY INTERVENTION

6.1 STUDY INTERVENTION ADMINISTRATION

6.1.1 Study Intervention Description

Use of BSS, which is lawfully marketed in the United States, is exempt from an investigational new drug application to the FDA in this study because its use meets the following criteria, per 21 CFR 312.2(b):

1. The investigation is not intended to be reported to FDA as a well-controlled study in support of a new indication and there is no intent to use it to support any other significant change in the labeling of the drug.
2. The investigation is not intended to support a significant change in the advertising for the drug.
3. The investigation does not involve a route of administration, dose, patient population, or other factor that significantly increases the risk (or decreases the acceptability of the risk) associated with the use of the drug products.
4. The investigation is conducted in compliance with the requirements for review by an IRB (21 CFR 56) and with the requirements for informed consent (21 CFR 50).

Abbreviated Title: BSS Gut Microbiome

Version Date: 05 July 2024

5. The investigation is conducted in compliance with the requirements of 21 CFR 312.7 (ie, the investigation is not intended to promote or commercialize the drug products).

6.1.2 Dosing and Administration

The oral suspension formulation of BSS will be used in this study. It is self-administered at 1050 mg 4 times per day (1 to 6 hours apart) for 2 days. The maximum dose in a 24-hour period is 4200 mg, which is consistent with the label.

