1.1 SYNOPSIS

Title:	An exploratory study of the effect of bismuth subsalicylate on the gut microbiome and host response in healthy adults
Study Description:	This is a single-site, single-arm, open-label study to evaluate the effect of bismuth subsalicylate (BSS) on the human gut microbiome and host immune response. Upon confirmation of eligibility, healthy adult volunteers will provide stool and optional blood, saliva, urine, and intestinal biopsy samples for a baseline assessment of gut microbiome and host immune response. Up to 18 weeks later, participants will undergo a 2-day/8-dose regimen of oral BSS. Stool will be collected at baseline, days 2 (+3), 8 (± 3), 14 ($-3/+7$) and 28 (± 7). Blood, saliva, and urine are also optional at these time points. Participants may also undergo a second optional colonoscopy at day 8 (± 3) to provide colon biopsies for research analysis.
Primary Objective:	To evaluate the effect of BSS on the human gut microbiome.
Secondary Objective:	To evaluate the effect of BSS on the human gut metabolome.
Tertiary/Exploratory Objective:	To evaluate the effect of BSS on the systemic and intestinal host response (immune and inflammatory responses).
Primary Endpoint:	Differences in the relative abundance of taxa in stool samples pre-BSS and approximately 1 month post-BSS. Differences in microbiome metrics of alpha diversity and beta diversity will also be assessed.
Secondary Endpoint:	Differences in the stool metabolome (including short chain fatty acids, bile acids, and untargeted metabolomics) pre-BSS and approximately 1 month post-BSS.
Tertiary/Exploratory Endpoint:	Differences in systemic host immune and inflammatory responses, such as cytokines and immune cells, and host intestinal immune responses, such as specific T-cell populations in intestinal biopsies pre-BSS and approximately 1 month post-BSS.
Study Population:	Healthy adult volunteers aged 18 to 50 years, n=20, accrual ceiling 40.
Phase:	N/A
Description of Sites/Facilities	NIH Clinical Center (CC), Bethesda, MD
Enrolling Participants:	
Description of Study Intervention:	BSS oral suspension, self-administered at 4 doses of 1050 mg each per day (1 to 6 hours apart) for 2 days. This is within the recommended adult dose.
Study Duration:	3 years
Participant Duration:	Up to 22 weeks.

Abbreviated Title: BSS Gut Microbiome

Version Date: 05 July 2024

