2.3 RISK/BENEFIT ASSESSMENT

2.3.1 Known Potential Risks

Bismuth subsalicylate: There are no adverse reactions listed in the manufacturer's labeling. The following adverse reactions have been reported in post-marketing and clinical trials of BSS for different indications:

- Temporary darkening/discoloration of the tongue and stool that resolves after discontinuation of the medication.(22) The exact frequency of this is unknown, but it is common enough to be listed on the Pepto-Bismol website.(23)
- Anaphylaxis (extremely rare, one case report).(24)
- Acute esophageal necrosis (extremely rare, one case report with chronic overuse of BSS).(25)
- Staining of teeth (rare and with chronic overuse of BSS).(26)
- Neurotoxicity and encephalopathy (extremely rare with chronic overuse of BSS).(26)
- Tinnitus (extremely rare with chronic overuse of BSS).(26)
- Salicylate toxicity in those who have taken BSS inappropriately, whether through an overdose or for extended periods of time.(27) Symptoms may include impaired cognition, tremors, lethargy, somnolence, insomnia, delirium, myoclonus, seizures, depressed mood, anxiety, and death.
- Other warnings/precautions: bismuth absorbs X-rays and may interfere with diagnostic procedures of GI tract.

In addition, some study participants have reported nausea while taking BSS.

Given the study hypothesis and the observations in BSS-treated mice, there is the possibility that BSS will affect the gut microbiome and immune response of participants. The magnitude and duration of such effects and their clinical significance, if they occur, are unknown.

There are potential interactions between BSS and other drugs, so use of these drugs will be prohibited during the study (sections 5.2 and 6.4).

Overall, the risks of BSS in the dose taken in this study are mild and temporary (darkening/discoloration of the tongue and stool) or extremely rare. Risks will be minimized by using the recommended dosing for 2 days only (no excessive or chronic dosing), excluding anyone with an allergy to BSS or other salicylates, and excluding those on medications that may have drug interactions with BSS.

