4.3 JUSTIFICATION FOR DOSE

The BSS dose chosen for this study of 1050 mg 4 times daily (about 1 to 6 hours apart) for 2 days is the recommended maximum dosage of the medication. This dose was chosen as it was within the recommended dose range, to maximize the potential effect, and to avoid adverse effects of overdosing or chronic dosing.

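### The frequency and interval rule in section 6.1.2 does not by itself deliver the 24-hour maximum of 4200 mg stated there; the two need reconciling

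*Combined protocol and SAP*

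**What the plan says.** Section 6.1.2 gives the regimen: "It is self-administered at 1050 mg 4 times per day (1 to 6 hours apart) for 2 days". The next sentence reads: "The maximum dose in a 24-hour period is 4200 mg, which is consistent with the label".

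The regimen is repeated elsewhere without a 24-hour limit. The synopsis (1.1) has "BSS oral suspension, self-administered at 4 doses of 1050 mg each per day (1 to 6 hours apart) for 2 days", and says that "participants will undergo a 2-day/8-dose regimen of oral BSS". Section 4.1 gives the same dose, frequency and spacing. Section 4.3 does so too, says that this "is the recommended maximum dosage of the medication", and gives avoidance of overdosing harms as one reason for the choice.

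The risk section (2.3.1) lists salicylate toxicity among the harms of inappropriate use and relies on the regimen as mitigation: "Risks will be minimized by using the recommended dosing for 2 days only (no excessive or chronic dosing".

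On timing, section 5.6.2 pays for the "in-person visit for first dose of BSS and completion of all 8 doses", and the Schedule of Activities makes day 0 an in-person visit. No clock time is given. Sections 3 and 9.1 treat day 2 as the day following treatment, which suggests dosing on days 0 and 1. No section defines *day* for dosing or states the gap between dose 4 and dose 5.

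The label will carry directions and cautions (6.2.2), participants receive measuring instructions (6.2.4), and reminders may be sent (5.6). The text of none of these is given. Compliance is self-reported (6.3), with no statement on whether dose times are captured.

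**The concern.** The regimen limits the number of doses per day and the spacing between them. The safety statement limits the amount in a 24-hour period. These are different constraints, and the first implies the second only if the second day's doses are far enough behind the first day's. Nothing in the frequency and interval rule requires that. Because the regimen already equals the stated maximum, one extra dose inside a 24-hour window exceeds it.

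At stake is a figure that the protocol gives as a property of its dosing. Sections 2.3.1 and 4.3 rely on dosing staying within the recommended amount. Participants are healthy volunteers who dose themselves after the first visit, so the written rule carries much of the weight.

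**Working it through.** **Inputs.** Dose 1050 mg; 4 doses per day; spacing 1 to 6 h; 2 days; stated maximum 4200 mg in 24 h (all 6.1.2). Total doses 8 (1.1).

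**The plan's own figure.** 4 × 1050 = 4200 mg, which reproduces exactly. The whole course is 8 × 1050 = 8400 mg.

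**Condition for the limit to hold.** Count doses in a window that includes its start and excludes the point 24 h later. No window holds more than 4 doses only if dose 5 comes at least 24 h after dose 1, dose 6 at least 24 h after dose 2, and likewise for doses 7 and 8.

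**An ordinary schedule.** Take 3-hour spacing with an assumed first dose at 13:00: 13, 16, 19, 22 h, then 07, 10, 13, 16 h. Dose 5 comes 18 h after dose 1 (11 h to midnight plus 7 h). The window from 13:00 holds 13, 16, 19, 22, 07 and 10 h: 6 × 1050 = 6300 mg, or 6300 / 4200 = 1.5 times the stated maximum. The overnight gap is 9 h, so this schedule applies the 1-to-6-hour spacing within each day only.

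**Range by reading of *day*.**

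| Reading | Rolling 24-h total the wording permits |
|---|---|
| Doses run on, every gap 1 to 6 h, no day boundary | 4200 to 8400 mg |
| Calendar day, overnight gap also 1 to 6 h (first dose assumed 08:00 to 17:00) | 5250 to 8400 mg |
| Calendar day, overnight gap free (same assumption) | 4200 to 8400 mg |
| Day is 24 h from first dose | 4200 to 7350 mg |
| 4200 mg sentence is itself a binding cap | 4200 mg |

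- *Run on.* Dose 5 follows dose 1 by four gaps, at most 4 × 6 = 24 h. The limit therefore holds only if every gap is exactly 6 h. Enumerating all 6^7 = 279,936 whole-hour schedules confirms that only this one stays at 4200 mg. With 3-hour gaps throughout, all 8 doses fall in 7 × 3 = 21 h: 8400 mg.
- *Calendar day, overnight gap 1 to 6 h.* With the first dose at 08:00 or later and the fourth by 23:00, dose 5 comes at most 15 + 6 = 21 h after dose 1. At least 5 doses then fall in 24 h: 5 × 1050 = 5250 mg. The upper end is reached by 10, 16, 20, 23 h, then 00, 01, 02, 03 h: 8 doses in 17 h.
- *Calendar day, overnight gap free.* Doses at 14, 16, 18, 20 h, then 07, 09, 11, 13 h put 8 doses in 23 h: 8400 mg, twice the stated maximum. The same clock times on both days (08, 12, 16, 20 h) keep to 4200 mg.
- *24 h from first dose.* Dose 5 comes no earlier than hour 24, so dose 8 comes no earlier than hour 27 and cannot share a window with dose 1. The ceiling is 7 doses. Hours 0, 6, 12, 18, 24, 25, 26, 27 reach it: the window from hour 6 holds 7 × 1050 = 7350 mg, 1.75 times the maximum.

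These schedules show what the wording permits. They say nothing about how often participants would dose this way.

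**The case against.** The strongest reply is that the 4200 mg sentence stands directly after the regimen, under the dosing heading, and can be read as a limit. A participant who took more than 4200 mg in 24 hours would then be departing from section 6.1.2. A reader might infer from the arithmetic that a fully compliant participant can take 8400 mg. The documents do not support that: it requires treating the sentence as commentary, and also a calendar-day or run-on reading. This part of the reply stands. It does not remove the problem, because a binding cap would forbid schedules that the interval rule allows, and sections 1.1, 4.1 and 4.3 give the regimen without the cap.

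Second, the operative instructions are not visible. The label, measuring instructions and reminders may already set a 24-hour limit, and the compliance form may already capture dose times. This also stands.

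Third, the documents do not say that first doses are taken late in the morning or in the afternoon. That is an assumption behind the clock-time examples.

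Two further inferences are tempting and should not be drawn:

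- *That the IND exemption fails.* The criterion in 6.1.1 is that "The investigation does not involve a route of administration, dose, patient population, or other factor that significantly increases the risk". Nothing here demonstrates a significant increase in risk.
- *That exposure is too uneven for the regimen to count as one treatment.* Consecutive gaps of 1 h and of 6 h give spans of 7 × 1 = 7 h and 7 × 6 = 42 h, but both apply the interval rule overnight, which the documents do not settle. The total is fixed at 8 doses, the primary comparison is about 1 month after BSS, and no effect on it has been shown.

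**Conclusion.** The point holds as an unreconciled pair of statements. The frequency and interval rule alone does not guarantee 4200 mg in any 24 hours under any of the definitions of *day* examined. Ordinary 3-hour spacing gives 6300 mg. The ceiling is 8400 mg or 7350 mg, depending on the definition. If the 4200 mg sentence binds, the inconsistency is between that cap and the schedules the interval rule permits.

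The conclusion assumes that a 24-hour period means any rolling 24 hours. The examples rest on assumed clock times. No participant has been shown to exceed the figure. Whether it agrees with the product label cannot be checked from the documents. The point still merits correction before participants dose under this wording: it bears on safety, sections 2.3.1 and 4.3 lean on the limit, and rewording is cheap.

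**What to change.** The sponsor should reconcile sections 1.1, 4.1, 4.3 and 6.1.2:

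- State whether 4200 mg is a binding limit, and whether it applies per calendar day or per rolling 24 hours.
- Define *day* for dosing and state how the gap between dose 4 and dose 5 is governed, so that the frequency and interval wording and the 24-hour figure agree.
- Use the same wording in the bottle directions, participant instructions and reminder messages, or confirm that they already carry it.
- Record the clock time of each of the 8 doses in the self-reported compliance record (6.3), if it is not already captured.

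Which rule applies is for the sponsor and its clinicians. The cost is protocol and label wording, eight time fields, and possibly less freedom for participants in when they take their doses.

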6.2 PREPARATION/HANDLING/STORAGE/ACCOUNTABILITY

6.2.1 Acquisition and Accountability

The study drug will be distributed and accounted for by the NIH pharmacy according to standard pharmacy procedures.

6.2.2 Formulation, Appearance, Packaging, and Labeling

The oral suspension is provided in bottles. The bottle label will include the following:

- Name and address of the dispensing pharmacy.
- Serial number of the prescription.
- Date of the prescription.
- Name of the patient.
- Name and strength of the drug.
- Directions for use.
- Appropriate cautionary statements.
- Name of the prescriber.

6.2.3 Product Storage and Stability

This information will be provided on the bottle's label.

6.2.4 Preparation

Participants will be provided with a bottle of BSS and instructions for measuring the correct dose.

6.3 STUDY INTERVENTION COMPLIANCE

Compliance will be self-reported via the Research Electronic Data Capture (REDCap) system, email, or telephone.

6.4 CONCOMITANT THERAPY

For this protocol, a prescription medication is defined as a medication that can be prescribed only by a properly authorized/licensed clinician. Medications to be reported in the Clinical Research Information System of the NIAID (CRIMSON) are concomitant prescription medications, over-the-counter medications, and supplements.

Participants will be advised to avoid taking BSS during study participation outside the defined study regimen so the effects of the study regimen can be accurately evaluated.

The following drugs have potential interactions with BSS, and thus will be prohibited from use during the study:

- Agents with antiplatelet properties (eg, P2Y₁₂ inhibitors, nonsteroidal anti-inflammatory drugs [NSAIDs], selective serotonin reuptake inhibitors): May enhance the adverse/toxic effect of salicylates. Increased risk of bleeding may result.
- Agents with blood glucose–lowering effects: salicylates may enhance the hypoglycemic effect of agents with blood glucose–lowering effects.
- Ajmaline: salicylates may enhance the adverse/toxic effect of ajmaline. Specifically, the risk for cholestasis may be increased.
- Ammonium chloride: may increase the serum concentration of salicylates.
- Angiotensin-converting enzyme inhibitors: salicylates may enhance the nephrotoxic effect of angiotensin-converting enzyme inhibitors. Salicylates may diminish the therapeutic effect of angiotensin-converting enzyme inhibitors.
- Anticoagulants: salicylates may enhance the anticoagulant effect of anticoagulants.
- Benzbromarone: salicylates may diminish the therapeutic effect of benzbromarone.
- Bismuth subcitrate: bismuth-containing compounds may enhance the neurotoxic effect of bismuth subcitrate.
- Carbonic anhydrase inhibitors: salicylates may enhance the adverse/toxic effect of carbonic anhydrase inhibitors. Salicylate toxicity might be enhanced by this same combination.
- Corticosteroids (systemic): salicylates may enhance the adverse/toxic effect of corticosteroids (systemic). These specifically include GI ulceration and bleeding. Corticosteroids (systemic) may decrease the serum concentration of salicylates.
- Dexketoprofen: salicylates may enhance the adverse/toxic effect of dexketoprofen. Dexketoprofen may diminish the therapeutic effect of salicylates. Salicylates may decrease the serum concentration of dexketoprofen.
- Ginkgo biloba: may enhance the anticoagulant effect of salicylates.
- Herbal products with anticoagulant/antiplatelet effects (eg, alfalfa, anise, bilberry): may enhance the adverse/toxic effect of salicylates.
- Hyaluronidase: salicylates may diminish the therapeutic effect of hyaluronidase
- Influenza virus vaccine (live/attenuated) within 2 weeks: may enhance the adverse/toxic effect of salicylates. Specifically, Reye's syndrome may develop.
- Loop diuretics: salicylates may diminish the diuretic effect of loop diuretics. Loop diuretics may increase the serum concentration of salicylates.
- Methotrexate: salicylates may increase the serum concentration of methotrexate.
- NSAIDs (nonselective): may enhance the adverse/toxic effect of salicylates. An increased risk of bleeding may be associated with use of this combination. NSAIDs (nonselective) may diminish the cardioprotective effect of salicylates. Salicylates may decrease the serum concentration of NSAIDs (nonselective).
- NSAIDs (topical): may enhance the adverse/toxic effect of salicylates. Specifically, the risk of GI toxicity is increased
- Potassium phosphate: may increase the serum concentration of salicylates
- Pralatrexate: salicylates may increase the serum concentration of pralatrexate. Salicylate doses used for prophylaxis of cardiovascular events are unlikely to be of concern.
- Probenecid: salicylates may diminish the therapeutic effect of probenecid.
- Salicylates: may enhance the anticoagulant effect of other salicylates.

- Sulfapyrazone: salicylates may decrease the serum concentration of sulfapyrazone.
- Tetracyclines: BSS may decrease the serum concentration of tetracyclines.
- Thrombolytic agents: salicylates may enhance the adverse/toxic effect of thrombolytic agents. An increased risk of bleeding may occur.
- Valproate products: salicylates may increase the serum concentration of valproate products.
- Varicella virus-containing vaccines within 2 weeks: salicylates may enhance the adverse/toxic effect of varicella virus-containing vaccines. Specifically, the risk for Reye's syndrome may increase.
- Vitamin K antagonists (eg, warfarin): salicylates may enhance the anticoagulant effect of vitamin K antagonists.

7 STUDY INTERVENTION DISCONTINUATION AND PARTICIPANT DISCONTINUATION/WITHDRAWAL

7.1 DISCONTINUATION OF STUDY INTERVENTION

Study intervention may be discontinued for an individual participant (ie, pausing), or it may be discontinued for all participants and enrollment suspended (ie, halting). Pausing and halting rules and procedures are described below.

7.1.1 Pausing Rules for an Individual Participant

Pausing is the suspension of administration of study agent to a single participant until a decision is made whether to resume administration of the study agent.

The pausing criteria for a single participant in this study include any of the following:

- A participant experiences a grade 3 or higher AE that is unexpected and is possibly, probably, or definitely related to the study agent or study procedures.
- A participant experiences an SAE that is unexpected and is possibly, probably, or definitely related to the study agent or study procedures.
- Any safety issue that the investigator determines should pause administration of the study agent to a single participant.

The principal investigator will determine if study agent administration should be paused.

